7.7.1. CMR sub-study assessments

Sub-study assessments will be performed according to the Schedule of Procedures, Appendix 4.

Height and weight

Full blood count (FBC): to be obtained at the time of the scan to permit measurement of extracellular volume. If it is not possible to obtain blood samples at time of scan, the FBC result from the main trial screening visit and/or week 16 visit will be used.

Cardiac MRI scans: To aid reproducibility, the CMR protocol should be constant for each participant. The participant should undergo CMR on the same scanner using the same acquisition protocol. Imaging may be performed at 1.5 Tesla or 3.0 Tesla field strength using a standard (e.g. 30-elements including 3 body and 2 spine) phased-array cardiac surface coil.

Participants will be advised to avoid caffeine containing drinks for 24 hours prior to the CMR examination. Wherever feasible, the CMR scan will be performed at approximately the same time of day on both occasions i.e. morning or afternoon.

The CMR scan will last approximately 1 hour. The participant will be given instructions regarding breath-holding and reassurance about the scan, particularly in relation to adenosine administration, prior to each scan.

Participants will have 2 intravenous cannulas inserted (one in each arm, for adenosine and gadolinium contrast administration).

During the scan injections of intravenous gadolinium contrast (up to 0.2 mmol/kg) and adenosine (up to 210mcg/kg/min) will be given. The participant will be given notice before any injections, and reassurance throughout the 2-3 minute duration of intravenous adenosine administration.

If a participant has had an adenosine stress CMR exam within 6 months of the baseline visit this can be used as the baseline scan if there has been no significant clinical change in the opinion of the local investigator

If CMR is not performed by the visit 3 window, then the visit 7 exam will not be performed.

The CMR will be reviewed by a trained reporter (e.g. a cardiologist or radiologist). Formal reporting will be performed as per local protocols. Participants will be informed of any clinically important findings in a timely fashion.

Heart rate, blood pressure: will be measured at rest prior to scan and during adenosine administration.

ECG monitoring: will be carried out during scanning as per routine CMR.

7.8. Review and recording of insulin management, blood glucose management, diabetic ketoacidosis and hypoglycaemia:

The majority of patients in the UK are provided with CGM systems (e.g. Flash CGM, Dexcom, Guardian) and capillary beta-ketone meters as standard care. Participants will all be provided with medical alerts (such as the STOP-DKA wallet card (see Appendix 6)) and where they don't already have them, blood ketone meters. In addition, some participants may have access to continuous ketone monitors during the trial. These will be supplied to all eligible trial participants, if available. A review of glucose and ketone management will be performed at each trial visit after screening by a local investigator or delegate. Review of glucose and ketone management may be delegated to an appropriately trained member of staff, for example a Specialist Diabetes Nurse. The final decision on management of glycaemic control and ketone management will be taken between the local investigator or delegate and the participant, however guidance is given here.

Participants should be managed in accordance with the recently developed position statements of the Association of British Clinical Diabetologists³⁹ and the International Consensus approach.⁴⁰ All participants will be carefully monitored throughout the trial and insulin dose adjustments made under the supervision of the research team as described below.

Participants will be specifically asked to check their glucose and ketone levels using their CGM and capillary beta-ketone meter as follows:

- In the 3 days before and after starting trial drug/placebo (i.e. before and after randomisation) participants should check paired glucose and ketone levels 4 times per day (e.g. before each meal and before bedtime), as well as 2 hours after changing each insulin giving set for those on insulin pump therapy. This will allow participants and investigators to obtain an understanding of baseline glucose and ketone levels and the response study drug/placebo.
- At least once weekly throughout the trial, ideally at the same time of day each week.
- If feeling unwell.

Participants may wish to check ketone levels any other time at their discretion or that of the local investigator.

Insulin Management:

Once randomisation is complete, individuals with an HbA1c <58mmol/mol at screening will have a 10% insulin dose reduction prior to taking their first dose of sotagliflozin/placebo. No reduction in insulin dose will be made for those with HbA1c ≥58mmol/mol at screening. All participants will then be advised to monitor regularly and to adjust insulin doses every 24-48 hours to achieve recommend blood glucose targets.

The total, basal and bolus doses of insulin used will be recorded for analysis for the 7 days prior to the trial visits at randomisation, week 4 and week 16.

Blood glucose management:

All participants will use CGMs that are supplied in the UK as standard care and data from these will be assessed at each visit by the local investigator or delegate. Participants who do not wish to use CGM will not be eligible to participate in the trial.

Where participants have a compatible CGM they will be asked if they wish to sign-up to free to use apps such as LibreView (Abbott) or Clarity (Dexcom). Participants create their own account and can download their blood glucose readings then give access to local investigators to view reports to assist with glucose management. Consent will be sought to share summary data from these reports and/or CGM recordings with the trial investigators. Participants who do not wish to sign-up to one of these apps will not be excluded from participating in the trial.

Investigators will recommend alarm settings on participants CGM to be set at a high alarm of 15 mmol/L (13 mmol/L if on an insulin pump) and a low alarm of 3.9 mmol/L. The lower alarm may be subsequently adjusted based on clinician and participant judgment and preferences. Alarm levels and CGM metrics should be assessed by the local research team at each visit.

CGM data will be entered into the data management system for trial analysis for the 2 weeks prior to the trial visits at randomisation, week 4 and week 16. Where available LibreView/Clarity etc. summary data will be used. The variables collected will include:

- Number of days CGM worn
- Percentage of time CGM is active
- Mean glucose
- Glycaemic variability (%CV).
- Percentage time in target, time above target and time below target.

Diabetic ketoacidosis (DKA):

Participants with type 1 diabetes should be aware of diabetic ketoacidosis. Further information on how to prevent, recognise, and treat DKA will be provided along with educational prompts. Participants will be also educated about precipitating factors for DKA (e.g. acute medical illness, vomiting, insulin pump failure, excessive carbohydrate restriction, excessive alcohol), when to discontinue therapy if these events occur and will be provided with contact details of the local research team and relevant emergency contacts for advice should any of these situations occur.

In addition to the above monitoring, participants will be advised to perform additional ketone testing if capillary/CGM glucose is >11.1 mmol/L for >2 hours or if feeling sick, according to standard sick day rules for diabetes management. Participants will be advised to check blood ketones if feeling unwell even when the capillary glucose levels are not particularly high, or with changes in diet, activity, insulin dose or events known to precipitate ketoacidosis and follow sick day rules as discussed with local team. If blood ketones are ≥ 0.6 mmol/L the clinician and participant will be encouraged to document reasons (e.g., alcohol, recent illness) for this and how it was managed. Advice will also be given regarding other times to check ketone levels (e.g., guidance is also given in Appendix 6 STOP-DKA protocol)⁴¹. Participants may be given a copy of the STOP-DKA guidelines, or local guidelines, dependent on local investigator's preference.

In summary the following strategies will be used to minimise DKA risk in addition to the educational measures:

- Participants will be asked to perform capillary ketone testing 4 times per day, 3 days before and 3 days after initiation of active drug/placebo, and 2 hours after changing each insulin giving set for those on insulin pump therapy as described earlier.
- Risk mitigation strategies, e.g. following the STOP-DKA Protocol if feeling sick or unwell with symptoms suggestive of impending DKA.

DKA will be defined as: blood ketone >3.0 mmol/l **and** blood pH of <7.3 or a bicarbonate <18 mmol/l.

Hypoglycaemia:

Hypoglycaemic events during the trial will be defined and documented as the following:

Level 1 hypoglycaemia (mild)	Measured plasma/capillary glucose concentration less than 3.9 mmol/L (70 mg/dL) but greater than or equal to 3.0 mmol/L (54 mg/dL). or CGM less than 3.9 mmol/L (70 mg/dL) but greater than or equal to 3.0 mmol/L (54 mg/dL) for at least 15 minutes
Level 2 hypoglycaemia (moderate)	Measured plasma/capillary glucose concentration less than 3.0 mmol/L (54 mg/dL). or CGM < 3.0 mmol/L for at least 15 minutes

Level 3 hypoglycaemia (severe)	
An event requiring hospitalisation and/or assistance of another person to actively administer carbohydrate, glucagon, or other resuscitative actions.
 
These episodes may be associated with sufficient neuroglycopenia to induce seizure or coma. Plasma glucose measurements may not be available during such an event, but neurological recovery attributable to the restoration of plasma glucose to normal is considered sufficient evidence that the event was induced by a low plasma glucose concentration.

--------------------------------	--

Participants will be asked to record the following:

- All level 2 and 3 hypoglycaemic events
- All symptomatic hypoglycaemia events for 2 weeks before baseline and at 14-16 weeks

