4.1. CMR sub-study design

A subset of participants (n=44) enrolled in the main SOPHIST trial will be invited to participate in a CMR sub-study at selected sites (including Dundee - the lead site for main trial and sub-study). Participants in the CMR sub-study will undergo CMR scans at baseline and after 16 weeks of treatment in addition to the standard trial assessments. CMR is intended to reflect the pre-treatment state and the effects of treatment in the preceding weeks.

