6.3. Exclusion criteria

1. Cardiac surgery (coronary artery bypass graft or valve replacement), type 1 myocardial infarction, implantation of cardiac device (including biventricular pacemaker) or cardiac mechanical support implantation within 1 month of screening, or between screening and randomisation, or planned during the trial.
2. End-stage heart failure requiring left ventricular assist devices, intra-aortic balloon pump, or any type of mechanical support at the time of randomisation.
3. Documented primary severe valvular heart disease, amyloidosis or hypertrophic cardiomyopathy as principal cause of heart failure as judged by the local investigator.
4. Respiratory disease thought to be the primary cause of dyspnoea as assessed by the local investigator.
5. Chronic kidney disease with estimated glomerular filtration rate $<25\text{ml}/\text{min}/1.73\text{m}^2$ at screening.
6. Moderate or severe hepatic impairment (e.g. Child-Pugh B and C) at screening as judged by the local investigator.
7. Use of sotagliflozin or any SGLT2 inhibitor within 1 month of screening or between screening and randomisation.
8. Previous hypersensitivity/intolerance to SGLT2 inhibitors.
9. Presence of malignancy with expected life expectancy <1 year at screening.
10. Severe hypoglycaemia (hospitalisation for hypoglycaemia or episode requiring external assistance to treat) within 1 month prior to screening or between screening and randomisation.
11. One episode of diabetic ketoacidosis or nonketotic hyperosmolar state within 1 month of screening or between screening and randomisation, or ≥ 2 diabetic ketoacidosis or nonketotic hyperosmolar state events within 6 months of screening.
12. Pregnant or lactating women.
13. Women of childbearing age or male partners of women of childbearing age and not practicing an acceptable method of birth control, see section 8.11
14. On a ketogenic diet.
15. Unwilling/unable to share glucose and ketone monitoring data.
16. Use of any investigational drugs within five times of the elimination half-life after the last dose or within 30 days, whichever is longer. Current enrolment in non-interventional, observational studies will be allowed.

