	Research Site	Remote/ Research Site	Research Site	Remote/ Research Site	Research Site	Remote/ Research Site	Research Site	Remote/ Research Site
Sub-study***								
CMR scan		X					X	
Height and Weight		X					X	
FBC		X					X	
Heart rate and blood pressure		X					X	

*The timing of the echocardiogram can vary as long as results are available in time for confirmation of participant eligibility at visit 3.

Dispensing may be delayed by up to 3 days to facilitate local practices. *CMR sub-study assessments may not necessarily be performed on the same day as the rest of the visit due to scheduling, some variation in the timing of the scan is acceptable. CMR will be performed within the following timescales:

- Baseline CMR scan: Day -30 to day 0.
- Visit 7 (week 16) – End of treatment scan. This can be performed up to 7 days prior to and 7 days after the scheduled visit 7.

[figure not shown]

Figure 1. Timing of CMR in relation to the main trial visits.

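### CMR sub-study: the six-month reuse rule for baseline scans does not agree with the Day -30 to 0 window, and the end-of-treatment scan may fall after treatment has ended

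*Protocol*

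**What the plan says.** **Baseline scan.** Section 7.7.1 begins by deferring to the schedule: "Sub-study assessments will be performed according to the Schedule of Procedures, Appendix 4". Appendix 4 accepts some variation in scan timing, then bounds it: "Baseline CMR scan: Day -30 to day 0". It mentions no other route to a baseline scan. Section 7.7.1 nevertheless adds one for existing scans, "adenosine stress CMR exam within 6 months of the baseline visit this can be used as the baseline scan", with the condition "if there has been no significant clinical change in the opinion of the local investigator". It also says that without a CMR by the visit 3 window there is no visit 7 scan.

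**Comparability.** The same section requires consistency within a participant: "The participant should undergo CMR on the same scanner using the same acquisition protocol". Field strength may be 1.5 or 3.0 Tesla.

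**Purpose.** Section 4.1 states: "CMR is intended to reflect the pre-treatment state and the effects of treatment in the preceding weeks".

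**Prior drug.** Section 6.3 excludes "Use of sotagliflozin or any SGLT2 inhibitor within 1 month of screening or between screening and randomisation".

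**Final scan.** Appendix 4 labels the week-16 CMR as an end-of-treatment scan and says: "This can be performed up to 7 days prior to and 7 days after the scheduled visit 7". Section 8.7 sets treatment at 16 weeks in total. Section 8.12 has tablets counted at visit 7, and no later supply is described.

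**The concern.** The sub-study's primary outcome (section 3.3) is the within-person change in global stress myocardial blood flow, so each result depends on what the two scans represent.

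At baseline, the governing schedule and the text of 7.7.1 give different answers for a scan that is, say, three months old. One site could accept it and go on to the week-16 scan. Another, following Appendix 4, could find no valid baseline and, under the visit 3 rule, not do the week-16 scan. The reuse sentence is also silent on SGLT inhibitor exposure at the time of the old scan and on whether rest perfusion was quantified. Rest flow and perfusion reserve are secondary outcomes.

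At follow-up, one window mixes scans taken on trial drug with scans taken after it has stopped, under a label and a stated purpose that point to treatment effect. If the effect on flow fades after the last dose, late scans would understate it.

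**Working it through.** **The plan's own figure.** Section 10.1 asks for 44 participants for 90% power to detect 0.71 mL/g/min, a value it describes as 1 SD. With SD 0.71 and two-sided alpha 0.05:

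n per group = 2 × (1.960 + 1.282)² × (0.71/0.71)² = 21.02, rounded up to 22, or 44 in total.

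The figure reproduces and is not in dispute. The point rests on calendar arithmetic.

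**Baseline window** (sections 7.7.1 and Appendix 4)
- Six months = 365.25/2, about 183 days, against 30 days in Appendix 4. The ratio is 183/30, about 6.
- The final scan may fall from Day 112 - 7 = 105 to Day 112 + 7 = 119.
- The interval between scans under Appendix 4 is 105 to 30 + 119 = 149 days.
- With a reused scan it can reach about 183 + 119 = 302 days.

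**SGLT2 inhibitor look-back** (section 6.3 and Appendix 4)
- Screening is Day -30 to Day -14. Taking 1 month as 30 days, the exclusion reaches back to between Day -60 and Day -44.
- The part of the six-month window that it does not cover is (183 - 60)/183 = 67% to (183 - 44)/183 = 76%.
- A scan in that part could have been taken on an SGLT2 inhibitor by someone who is now eligible. The Protocol does not say how many such people there may be.

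**Final scan against treatment** (sections 8.7, 8.12 and Appendix 4)
- Sixteen weeks = 112 daily doses. With the first dose on Day 0, the last scheduled dose is on Day 111.
- The latest scan is on Day 119, a gap of 119 - 111 = 8 days.
- If dispensing is delayed by the permitted 3 days and all 112 doses are taken, the last dose is on Day 114 and the gap is 5 days.
- If visit 7 is held 3 days early (Day 109), drug stops there and the window is still counted from Day 112, the gap is 10 days.
- Scans from Day 105 up to the last dose are on treatment, so only the later part of the window is affected.

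**The case against.** The strongest reply on baseline is that the two texts are a general rule and an exception: Appendix 4 says when a trial scan is performed, and 7.7.1 says when an existing scan may stand in. The Protocol reuses earlier echocardiograms and NT-proBNP results in the same spirit. That is a fair account of what was probably meant. However, those rows of the schedule are marked as needed only if required. The CMR row is not, and the stated timescales carry no exception, so the texts still have to be reconciled.

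Several stronger readings are tempting, and the Protocol does not support them:
- **That any six-month-old scan is accepted.** It is not, because the investigator must see no significant clinical change. That condition does not address drug exposure or acquisition.
- **That reuse waives the same-scanner rule.** Nothing says so. An incompatible old scan fails the existing text, and the only weakness is that the reuse sentence does not repeat the rule.
- **That the follow-up rules contradict each other.** There is only one follow-up window. It sits badly with its label, and the reference in section 4.1 to treatment in the preceding weeks tolerates a short gap.
- **That prior SGLT2 inhibitor use biases the comparison between arms.** Such exposure precedes randomisation and is balanced in expectation. It adds noise.
- **That power falls by a stated amount.** The Protocol gives no offset time for myocardial blood flow and no correlation between scans. Suppose older baselines lowered the correlation to 0.3 (assumed). The baseline-adjusted SD would be 0.71 × √(1 - 0.3²) = 0.68 mL/g/min, still below the planning SD of 0.71. Power with 22 per group would be 92.5%, above the planned 90%.

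It also stands that tight windows have a price. Confining reuse to Day -30 to 0 would repeat gadolinium and adenosine exposure, and ending the final window at visit 7 would risk losing scans.

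**Conclusion.** The point holds as a matter of wording and measurement quality. Section 7.7.1 and the schedule it defers to disagree on how old a baseline scan may be, about 183 days against 30. The reuse condition does not ensure a scan free of SGLT inhibitor effect. The final scan can fall about 8 days after the last scheduled dose, assuming a first dose on Day 0 and no missed or delayed doses, with 5 to 10 days under the variations shown.

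The consequence is extra noise in the change score and possible dilution of a treatment effect. Neither can be sized from the Protocol, so no power loss should be quoted. The sample size of 44 is not wrong on this account, and only the sub-study is touched. The baseline part is the firmer of the two. The follow-up part is a window that fits poorly with the scan's own label and purpose.

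**What to change.** 1. **Reconcile section 7.7.1 and Appendix 4 on the baseline window.** Either Appendix 4 carries the reuse exception or 7.7.1 drops it.
2. **If reuse is kept, attach conditions.** Accept an earlier scan only if it was on the same scanner, used the same quantitative stress and rest acquisition as the week-16 scan, and was taken with no SGLT inhibitor use. Otherwise do the scheduled baseline scan.
3. **Final scan.** Book it on or before the last tablet where possible, and record days since last dose for every final scan. The existing outer limit can stay, so that late scans are not lost.
4. **Analysis.** Examine scans taken after treatment ended in a sensitivity analysis. The SAP is the natural place for this.

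The cost is a wording amendment, one extra data field and somewhat tighter booking. A few participants would have the scheduled baseline scan, with its contrast and adenosine, where they might otherwise have reused an earlier one.

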8.7. Dosage schedules

Participants will take one 200mg tablet of Sotagliflozin/matched placebo daily for a total of 16 weeks, usually before breakfast. If the participant misses a dose of the trial drug by less than 6 hours, they should still take it when remembered and then continue all subsequent doses as scheduled. If a participant misses a dose by more than 6 hours after it was scheduled then they should skip that dose and only take their next dose at their next scheduled time (i.e. the next day before breakfast).

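### Section 7.8 treats drug start and randomisation as the same event, but Appendix 4 lets dispensing lag by up to 3 days, so the scheduled post-start ketone testing can be shortened or finish before the first tablet

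*Protocol*

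**What the plan says.** Four statements in the Protocol bear on when the intensive testing takes place.

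- **Section 7.8, monitoring list.** "In the 3 days before and after starting trial drug/placebo (i.e. before and after randomisation) participants should check paired glucose and ketone levels". The frequency is four times daily, with additional checks after giving-set changes for pump users. The purpose follows directly: "This will allow participants and investigators to obtain an understanding of baseline glucose and ketone levels and the response study drug/placebo".
- **Section 7.8, DKA risk summary.** The same four-times-daily testing is listed as a strategy to reduce DKA risk, timed as "3 days before and 3 days after initiation of active drug/placebo". Randomisation is not mentioned.
- **Section 7.8, Insulin Management paragraph.** The sequence given there is: "Once randomisation is complete, individuals with an HbA1c <58mmol/mol at screening will have a 10% insulin dose reduction prior to taking their first dose". Randomisation and first dose are separate steps here, with an insulin change between them for some participants.
- **Appendix 4, Schedule of Procedures.** Randomisation and dispensing both sit at Visit 3, Day 0, but a footnote adds: "Dispensing may be delayed by up to 3 days to facilitate local practices".

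Section 8.7 has the tablet taken "daily for a total of 16 weeks, usually before breakfast". Outside the intensive window, the scheduled minimum in section 7.8 is "At least once weekly throughout the trial, ideally at the same time of day each week".

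**The concern.** The parenthesis in the monitoring list is true only if the drug is dispensed and started on the day of randomisation. The Appendix 4 footnote allows otherwise, and the permitted delay is as long as the whole post-start testing window (3 days in each case). A site can therefore comply with every sentence it reads and still place much or all of the post-start testing before the drug is taken.

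Two things are at stake. The testing is meant to show both the untreated levels and the response to study drug, and the second half fails if it ends too early. It is also one of the two strategies that section 7.8 lists, beyond education, to limit DKA. The Protocol treats DKA as a key risk: section 2.1 cites 2.7% on sotagliflozin 200 mg against 0.5% on placebo in earlier trials, and section 3.2 makes it a safety outcome.

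**Working it through.** The Protocol gives no figure to reproduce, so this is a day count.

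**Inputs**
- Randomisation is day 0 (Appendix 4).
- Dispensing is on day L, with L = 0, 1, 2 or 3 (Appendix 4 footnote).
- The first tablet is on day F. Either F = L (taken on the day of dispensing) or F = L + 1 (taken the next morning, which is plausible because section 8.7 has dosing usually before breakfast).
- Testing is 4 checks a day for 3 days after the anchor, so 4 × 3 = 12 scheduled checks (section 7.8).

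**Counted from randomisation (the parenthesis).** The post-anchor testing days are days 1 to 3.

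Full testing days after the day of the first tablet = max(0, 3 − F), and checks = 4 × that number.

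| Delay L | F = L: full days (checks) | F = L + 1: full days (checks) |
|---|---|---|
| 0 | 3 (12) | 2 (8) |
| 1 | 2 (8) | 1 (4) |
| 2 | 1 (4) | 0 (0) |
| 3 | 0 (0) | 0 (0) |

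The zeros differ in meaning. Where F = 3 (L = 3 with a same-day tablet, or L = 2 with a next-morning tablet), the last testing day is the day of the first tablet, so some checks that day may follow it. Only L = 3 with a next-morning tablet gives F = 4, one day after testing ended on day 3. That is the one case in which no scheduled intensive check can follow the first dose.

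**Counted from drug start (the main clause and the DKA summary).** The post-anchor days are F + 1 to F + 3, which gives 3 full days and 12 checks for every L.

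**The days before.** Counted from randomisation, the pre-start window closes on day 0. At L = 3 that is 3 days (F = 3) or 4 days (F = 4) before the first tablet. Baseline information is not lost, because the checks on days 1 to 3 made before the first tablet are also untreated. What is lost is the on-drug half.

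**The case against.** The best reply is that the monitoring list already names the right kind of event. Its main clause refers to starting the trial drug, as the DKA summary does, and the stated purpose points the same way. On this view the parenthesis is a loose gloss that a sensible site would ignore. Much of this stands: a reader might infer that section 7.8 sets two rival windows, one from randomisation and one from first dose, and the text does not support that. The conflict lies inside one sentence, and between that sentence and the Appendix 4 footnote. The gloss is nevertheless written as an equivalence, and nothing tells a site with delayed dispensing which half to follow.

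Three further inferences also go too far.

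- *Testing routinely finishes before the first tablet.* This needs the parenthesis to be followed, the full 3-day delay and a next-morning first tablet. Shorter delays mostly shorten the post-start testing.
- *The first days on drug have no ketone data.* Weekly checks continue. Section 7.8 also advises checks when unwell, when glucose stays above 11.1 mmol/L for more than 2 hours, and when insulin dose changes. The last of these applies to participants given the 10% insulin reduction. Only the scheduled intensive checks are at risk.
- *Visit 4 is mistimed and must be moved.* All visits in Appendix 4 are counted from Day 0. Visit 4 at day 4 to 10 would be 1 to 7 days after a first tablet on day 3, but its ±3-day window already spreads exposure by 6 days, and moving it alone would leave a mixed schedule. That is a preference, not an inconsistency.

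**Conclusion.** The point holds as an inconsistency of wording with a practical safety-monitoring consequence. Under permitted conduct, a site that follows the parenthesis retains 12, 8, 4 or 0 of the 12 scheduled checks on full days after the first-tablet day, for delays of 0 to 3 days with a same-day first tablet. In the extreme case the window closes before the first dose.

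This rests on three assumptions: that some sites use the dispensing allowance, that some of them follow the parenthesis rather than the main clause, and that the three days after the anchor are days 1 to 3. The Protocol does not say how often delayed dispensing is expected, so the number of participants affected cannot be estimated.

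The primary endpoint, its analysis and the sample size are untouched. The exploratory ketosis outcome in section 3.2 is set at weeks 0 and 16 and does not depend on this window.

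**What to change.** Reconcile the monitoring list and the DKA risk summary in section 7.8 with the dispensing footnote in Appendix 4, so that one anchor for the intensive testing window is stated and used throughout. The wording should make clear how the window meets its stated purpose, baseline levels and response to study drug, when dispensing is delayed. The Insulin Management paragraph should be read alongside, so that the order of randomisation, insulin step and first dose is consistent with the chosen anchor. The choice of anchor is the sponsor's; no change to dose, testing frequency, insulin rule or visit schedule is proposed here.

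The cost is a wording amendment and a short note to sites.
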